9.5.2 Secondary Outcome

The secondary objectives of this study are to: develop a responsive acupuncture intervention and

assess implementation in emergency departments associated with 3 BraveNet research sites for acceptability and fidelity. This study will include qualitative interviews and structured observation to assess feasibility of implementation.

To evaluate implementation of the acupuncture intervention, using both quantitative data (study records, stakeholder surveys) and qualitative data (interviews and observations), we base our selection of implementation outcomes on the synthesis and recommendations outlined by Proctor et al in their authoritative 2011 paper.⁸⁶ We include all of the early phase outcomes, excluding cost, proposed in this widely cited framework, including: Feasibility (“practicability”), provider adoption, perceptions of appropriateness, acceptability, and treatment fidelity. These will be assessed both quantitatively and qualitatively. In addition to implementation outcomes, we will also examine implementation processes, strategies, stakeholder experiences, and barriers and facilitators to implementation using both qualitative interviews and real-time observations.

Structured Observation

Observations will be focused largely on the influences of actors and contextual factors on implementation uptake/feasibility. Examples could include: disruptive behavior or manifestations of severe illness/pain; staff strategies to mitigate or address these in order to facilitate treatment uptake; provider statements or interactions that interfere with uptake; environmental variables (a ‘slow night’ in the ED that results in extra rooms to be used for the intervention, or the difference between a weekend and weekday night); etc. Observation notes will form the basis of a complete detailed field observation to be analyzed along with interview data using the strategies described below.

Qualitative Interviews

We will use a semi-structured interview guide that focuses on likely implementation barriers and facilitators, including: interactions and communications with the research team, patient flow, burden of the intervention, perceived need and benefits of the intervention, etc. As described above, we will use the domains of the Consolidated Framework for Implementation Research (CFIR)⁸⁷ to organize the topic guides that will be developed for the qualitative interviews. Interview recordings will be stored to a secure server and interviews will be professionally transcribed.

9.6 Data Analyses

Aim 2: Conduct a feasibility RCT to examine the feasibility of data collection, intervention implementation and treatment outcomes overall and across sites.

Aim 2a. Evaluate the feasibility of research procedures, including data quality completeness, and participant recruitment and retention, using study records

Overall Approach. Using study records and administrative data we will track recruitment (proportion of eligible patients recruited), document recruitment rates (time to recruit intended sample), and rates of loss to follow up. Data collection forms collected at each time point will be evaluated for quality and completeness. In addition, all quantitative data analyses will be preceded by extensive data checking and verification to identify and resolve the reasons for missing values, inconsistencies, and out-of-range values. Although we anticipate some missing data based on our experience, we will carefully examine whether missingness is completely at random (MCAR), at random (MAR) or informative (MNAR).

Models proposed for analysis can handle incomplete data but do require at least that missingness be at random. Modelling will consider using multiple imputation techniques of covariates to reduce potential biases. To assess recruitment, we will track the number of eligible patients presenting to the ED and the proportion who agree to participate. Basic demographics and presenting complaint will be collected for all eligible patients, allowing us to identify subgroups who are more or less likely to participate. Similarly approaches will be used to assess rates of loss to follow up at all data collection points. We will assess variables across different patient groups (including age, race, sex), and across the study arms as well as overall and by sites.

Aim 2b. Evaluate the implementation of the acupuncture intervention, using both quantitative data (study records, stakeholder surveys) and qualitative data (interviews and observations).

Overall approach. We base our selection of implementation outcomes on the synthesis and recommendations outlined by Proctor et al in their authoritative 2011 paper.⁸⁶ We include all of the early phase outcomes, excluding cost, proposed in this widely cited framework, including: Feasibility (“practicability”), provider adoption, perceptions of appropriateness, acceptability, and treatment fidelity. These will be assessed both quantitatively and qualitatively. In addition to implementation outcomes, we will also examine implementation processes, strategies, stakeholder experiences, and barriers and facilitators to implementation using both qualitative interviews and real-time observations. For a list of implementation constructs, variables, and data sources, see Table 1.

Table 1: Implementation Variables and Sources

Construct	Variable	Data Collection/Source
Outcomes		
Feasibility		
• Recruitment • Uptake	# recruited patients / # eligible # completed sessions /# recruited	Study records Provider assessment, real-time observations, qualitative interviews
Adoption	# approved / # recruited	Study records
Appropriateness	Suitability for ED setting	1 item survey, qualitative interviews
Acceptability	Satisfaction/helpfulness	1 item survey, qualitative interviews
Fidelity	Adherence to Responsive Manualization	[name] reviews study records and discusses with study acupuncturists
Stakeholder strategies	Processes and steps taken	Qualitative Interviews
Barriers and facilitators	Strengths/weaknesses of the program Contextual influences at patient, provider, local, and institutional level	Qualitative interviews/structured observation

Aim 2b1. Assess Implementation outcomes: feasibility, adoption, appropriateness, and acceptability.

Feasibility is defined as the degree to which AC can be successfully implemented in the ED setting. This is operationalized as **recruitment** (see Aim 2a); and **uptake** (the proportion of recruited patients who receive a complete AC session, measured by a single question assessment: “*Did patient xx receive a completed treatment session at this visit?*”). Feasibility of the study will also be assessed qualitatively, through stakeholder interviews focusing on barriers and facilitators to implementation, and real-time observations of the uptake of the intervention in the ED setting. For a description of qualitative data collection and analysis, see section 2b2 below.

Provider adoption is defined as the intention to engage with the innovation/intervention. This is operationalized as the proportion of an ED physician’s recruited patients who are approved for study participation. As elsewhere, we will assess variables across different provider characteristics (including age, race, sex), overall and across the study sites to assess group differences in this outcome and those below.

Perception of appropriateness is defined as the perceived **suitability** of the intervention to the ED setting. ED providers will be asked: “*To what degree do you view the acupuncture intervention as useful or suitable for this ED setting?*” (1-very appropriate—5-Very inappropriate); Perceptions of appropriateness will also be explored through qualitative interviews.

‘Acceptability’ is defined as perceptions of the palatability of an innovation, or satisfaction by stakeholders with aspects of an innovation. It is more specific than overall satisfaction with a service.⁹⁹ For this study, acceptability among ED staff is operationalized in our quantitative assessment as satisfaction with the acupuncture intervention as delivered in the ED setting. **Providers** will answer two questions regarding their general opinion about acupuncture: “Do you view acupuncture in general as an appropriate intervention for the ED setting?” Likert scale (1-very appropriate—5-Very inappropriate) and “Do you view acupuncture in general as helpful in managing patient pain in the ED?” Likert scale (1-Very helpful—5- Not at all helpful). And two questions regarding the delivery of ACUITY study in the ED: “Were you satisfied with how the ACUITY acupuncture intervention was delivered in your setting?” Likert scale (1-Very satisfied—5-Very dissatisfied) and “Did the ACUITY project impose a burden on ED staff in your setting?” Not a burden, Somewhat of a burden, Moderate burden, Extreme burden.

Acceptability of the intervention will also be explored in depth in semi structured stakeholder interviews.

‘Fidelity’ in this study is defined as the proportion of patients who are treated in a manner consistent with the manualized intervention. The exact treatment fidelity parameters will be determined by consensus of acupuncture experts in accord with Aim 1. We expect that the treatment fidelity measures will include: the dose (minimum number of needles, minimum number of points treated, minimum duration of needle retention time), and the session delivery (was the intervention delivered as planned or cut short due to ED flow). [name] will review the chart documentation of all acupuncture interventions and assess manual fidelity. She will assess the proportion of cases where acupuncturists treated the patient ‘off manual’ (and why), as well as assessing whether minimum standards for number of needles used, points treated and needle retention time were met. Assessment will be across different practitioners, times of day, sites, and by participant demographics (e.g. sex) and presenting complaints.

Aim 2b2. Assess implementation processes, strategies, and barriers/facilitators to implementation using semi structured stakeholder interviews and structured observations

Overall approach for qualitative data collection in Aim 2b1 and 2b2.

We will conduct **qualitative interviews** with a broad range of relevant staff stakeholders (n~10/site), including ED providers, ED staff, and acupuncturists. A second component is **field observation** in participating EDs.

[name] will conduct structured observations at each of the three sites during one 2-day field visit to each site, observing the implementation of acupuncture in the ED in real time. The observations will be recorded in detailed field notes and transcribed into a full description when the observation is complete.

Lessons learned from field observation and preliminary analysis of process implementation at each site may inform implementation at subsequent sites.

The success of program implementation depends on many factors, as described in Damschroder, et al’s influential CFIR framework.⁸⁷ The CFIR includes 5 ‘domains’ influencing implementation: the intervention, inner and outer setting, individuals, and processes. We will use the CFIR domains to structure our inquiry and to make sure that our qualitative data collection instruments, coding system, and interim reports reflect the complex multiple levels of influence that will shape the conduct and outcomes of the acupuncture intervention. We provide some examples of how CFIR domains will be operationalized as interview topics in the Table 2.

Table 2: CFIR Domains of Influence/Topics/Sample Questions

CFIR Domain	Sample Interview Guide Topics	Sample question
Intervention	Complexity Burden Need/utility	How useful was this intervention? How difficult was it to get it going in the ED? What was the burden and who bore the burden?
Individuals	Stakeholder Characteristics, attitudes, perceptions/The Pain Episode	How receptive were patients/nurses/front desk staff, etc. to the intervention?
Outer Setting	The larger political/historical context Socio-economic factors	How has the opioid epidemic influenced your views of the Acupuncture intervention? How do socioeconomic factors influence your patients' pain and other treatment needs?
Inner Setting	Characteristics of the ER such as norms, values, readiness for change Crowding/staffing/pace/other resources	How receptive were ED staff to this intervention? Why? What time of day/day of week was it easiest to implement the Acupuncture intervention? Most difficult? How did communication among staff influence the implementation
Processes	Stakeholder strategies and processes	What was your process in planning for this intervention? Whose help was needed in moving this intervention forward and how did you engage them?--What efforts did the Champion make to move this forward?

Qualitative Interview Methods.

Stakeholder sample. We will recruit a sample at each site that reflects key stakeholders, including both staff and patients, at that site. The **staff stakeholder** list will be prepared in consultation between project leadership and local collaborators. It will include the physician/providers whose patients were included in the trial, nurses and other medical providers, and the acupuncturist, and may include study staff. A purposive sample of patient stakeholders will be recruited to reflect the diversity of patients assigned to the intervention. Patients who received acupuncture (n~15 per site) will be purposefully sampled to include multiple presenting complaints and both sexes, as well as older and younger patients. In keeping with good practices in qualitative research, sample sizes are not determined in advance. Sample sizes are determined by the emergence of data saturation, when no new themes arise in the analysis.

Interview guide. We will develop a semi-structured interview guide that focuses on likely implementation barriers and facilitators, including: interactions and communications with the research team, patient flow, burden of the intervention, perceived need and benefits of the intervention, etc. As described above, we will use the domains of the CFIR to organize the topic guides that will be developed for the qualitative interviews. Interview recordings will be moved from the handheld digital recording device to a secure server immediately after each interview. Interviews will be professionally transcribed.

Structured Observation Methods.

Observational data provides an important perspective that differs from that of individual interviews. While interviews permit an in-depth exploration of reasoning, motives, and perspectives, they are also highly vulnerable to various types of bias. Observational data, by contrast, provides powerful, real time evidence regarding stakeholder behaviors and interactions within the local environment. During a 2-3-day site visit to each site, the Implementation Team leader, [name], will conduct structured observations of protocol implementation. The length and timing of each observation will be determined through consultation with project leadership and local staff. If possible, observations will be conducted at different times reflecting the normal ebb and flow of patient care at the local site. Daytime, night, weekend, and week day observational periods will be included as feasible in the sample. Observations will be focused largely on the influences of actors and contextual factors on implementation uptake/feasibility. Examples could include: **disruptive behavior** or manifestations of severe illness/pain; **staff strategies** to mitigate or address these in order to facilitate treatment uptake; provider statements or **interactions** that interfere with uptake; **environmental variables** (a 'slow night' in the ED that results in extra rooms to be used for the intervention, or the difference between a weekend and weekday night); etc. Following the observation, the report form will form the basis of a complete detailed field observation will be analyzed along with interview data using the strategies described below.

Analysis of Aim 2b. To analyze qualitative interview and observational data, we will use QSR's NVivo, a computer program that facilitates 1) the rapid organization and retrieval of thematically linked data; and 2) the use of quantitative grouping variables to classify cases and generate complex comparisons. Interview and observational data will be transcribed and uploaded into a case library organized by site. In a first step, we will conduct a thematic qualitative analysis. First, a preliminary coding scheme will be developed, based on the framework. The scheme will then be applied to a subset of the data by members of the Implementation Team. Any differences in coding decisions will be discussed, and the coding scheme will be revised as needed. This process will be repeated on a second subset of the data, and the coding scheme subsequently revised in an iterative process until it is judged sufficiently accurate and comprehensive. At this point, the data will be uploaded into NVivo and coded by members of the team. Memos will be created for each interview describing the major themes emerging in the transcript. Memos will be used to determine the emergence of data saturation, described above.

Next, the coded data will be retrieved and used to create case summaries of key themes related to implementation processes at each site. The matrix functionality in NVivo will be used to conduct comparative analyses both within and across sites. *Within site analyses* will include comparisons of relevant groups. For example, we will compare different sexes and ethnic groups of patients in terms of their perceptions of the intervention. Examples of comparisons include: younger vs. elderly patients; night observations compared to day observations; weekday observations vs weekend observations. In the *cross site analyses*, we will examine differences in barriers, facilitators and implementation processes across the three sites with the goal of generating inferences regarding the important factors shaping differences in implementation outcomes. For example, presuming that the sites differ on rates of recruitment, we will examine our qualitative data to generate hypotheses regarding the causes of this documented difference. Similarly, sites that succeed better with recruitment, retention, or fidelity to the intervention will be compared to sites that are less successful.

Mixed methods analysis. Quantitative and qualitative data collected in Aim 2 will be integrated in a mixed methods analysis. We will use findings from the quantitative survey questions to create comparison groups for qualitative analysis. For example, providers who judge the protocol as 'acceptable' will be compared to those who do not. We will conduct comparative analyses to understand how qualitative themes are associated with these implementation outcomes.

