2.2 Study Rationale

PRELIMINARY DATA

Observational Study 1: Abbott Northwestern Hospital Emergency Department (ANW ED)

Using supplemental funding from his R01 NIH grant (1R01AT006518), [name] conducted an observational study of acupuncture in the ED.⁵¹ Acupuncture was available for about 15-20 hours per week from November 2013 to December 2014 in the 35-bed ANW ED. Acupuncture was provided by a licensed acupuncturist upon referral of ED physicians or mid-level providers. The primary outcome was change in pain intensity from before to after acupuncture using a 0-10 verbal NRS pain scale.^{58,59} The 0-10 NRS is commonly used in the ED, and scores correlate with the visual analog scale.⁶⁰ It has also been used in clinical trials.⁶¹ Anxiety was also measured on the NRS at the same time. The acupuncturist collected pain and anxiety scores before/after acupuncture via an EPIC-based flowsheet used in [name]'s R01 study of acute patients.⁶²⁻⁶⁴

Results: Acupuncture was well-accepted by providers: 73% referred at least one patient for acupuncture during the study period. Of 436 patients referred, 279 were approached by the acupuncturist during their ED visit. Informed consent was obtained from 89% (248/279) of patients. The final sample consisted of 182 patients presenting with acute pain who received acupuncture and had a post-treatment score. The sample was representative of the overall ANW ED population: average age was 45.3 (16.7 SD), 67.6% were female and 39.0% were non-white. In the final sample, 49% (88/182) of patients received pain medications prior to acupuncture and reported a mean of 6.88 on the pain pre-treatment score and a 30-min post-treatment change of -2.68 units (SD 2.23). In comparison, 51% (94/182) received no pain medications before acupuncture and reported 6.71 on the pain pre-treatment score and a 30-min post-treatment change of -2.37 units (SD 2.23). As a -2.0 unit decrease in pain on NRS is considered clinically significant,⁶⁵ patients in both groups exceeded this threshold. Finally, across both groups, the pre-treatment anxiety score was 4.73 (3.43 SD) and the 30-min post-treatment change was -2.27 units (SD 2.66). Pain and anxiety change scores were correlated ($p=0.004$).

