6.2 Description of Evaluations

6.2.1 Screening Evaluation

At each ED, the Study Coordinator (SC) or Research Assistant (SC) and acupuncturist will work as a team, staffing an average 2.5, 4-6 hour recruitment/intervention sessions per week, varying the times

and days across sites as this may influence adoption. As in Figure 1, after the ED RN conducts the initial triage activity, the SC or RA (“study staff”) will identify and conduct initial eligibility pre-screening in the in the ED triage unit. The patient will then be roomed and seen by the ED clinical provider. If the ED provider determines that patient does not have a clinical condition prohibiting study participation, s/he will sign a study approval form (see below). The study staff will then approach the patient for study participation.

Provider sign off

Acupuncture in the Emergency Department for Pain Management (ACUITY)

If the patient is randomized to the acupuncture arm, please withhold pain and anxiety medications until after the acupuncture session.

The study coordinator will inform you what arm they are assigned to and when their session has ended.

In order for this patient to be eligible to participate in the "Acupuncture in the ED" study, please verify you have examined the patient and believe to the best of your knowledge, at this time, that the patient does not have the following conditions:

Critical status / Trauma
 Bone fracture
 Joint dislocation
 Migraine
 Psychological / psychiatric concern
 Clinical judgement / Other:

If you deem the patient eligible for the study, the patient will be randomized to acupuncture or usual care.

Patient can continue in study
 Patient is excluded from study

Sign: _____

Consenting Procedure

We have requested a partial HIPAA waiver for prescreening. Therefore, patients will only be consented once the screening process is over and eligibility is confirmed.

The consent process will occur after the patient has gone through the triage process and been assigned to a room within the ED. The consent process will be conducted by dedicated research staff (SC or RA) that have been trained in obtaining informed consent and who have current Human Subjects Protection and Good Clinical Practice certifications. The status and location of the patient will be monitored by

research staff using the EHR to ensure the patient is approached at an appropriate time.

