9.5 Outcomes

Implementation and Treatment Outcomes

All data analyses will be preceded by extensive data checking and verification to identify and resolve the reasons for missing values, inconsistencies, and out-of-range values. Although we anticipate little missing data based on our experience, we will carefully examine whether missingness is completely at random, at random or informative. Models proposed for analysis can handle incomplete data but do

require at least that missingness be at random. Descriptive statistics of primary outcomes: pain intensity change scores for Pre-Treatment to Post-Treatment and Pre-treatment to ED Discharge as well as secondary outcomes will be conducted to assess their distribution overall and by sites as well as demographic characteristics (e.g. sex, age group, race, household income, pain location among others). The variables will be summarized using descriptive statistics (sample size, mean, standard deviation, median, minimum, and maximum) for continuous variables and by the number and percentage of patients for categorical variables. We will report 95% exact confidence interval of median⁸³ for the key continuous variables and 95% exact binomial confidence interval⁸⁴ for categorical variables. All assessments will include sex as a biological variable as described below.

Feasibility of Recruitment and Retention

We will assess recruitment rates (# enrolled / # eligible), pace of accrual, data completeness, and retention at each data collection point, overall and across sites. We will assess variables across different patient groups (including age, race, sex), and across the study arms. Provider adoption will be assessed by the proportion of their eligible patients that clinicians approve for study participation. We will assess variables across different provider characteristics (including age, race, sex), and across the study sites. Completeness of data collection and retention at each time point: we will also track completeness of data collection, and patterns and proportions of missing data at each time point. We will compare these proportions overall and across sites and by demographics as described above.

Acceptability

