9.5.1 Primary Outcome

The primary objective of the current protocol is to conduct a feasibility RCT to examine the feasibility of refined data collection procedures, and examine intervention implementation and treatment outcomes across sites. As well as, evaluate the feasibility of research procedures, including data quality completeness, participant recruitment and retention, and using study records.

Data Completeness

Using study records and administrative data, we will track recruitment (proportion of eligible patients recruited), document recruitment rates (time to recruit intended sample), and rates of loss to follow up. Data collection forms collected at each time point will be evaluated for quality and completeness. In addition, all quantitative data analyses will be preceded by extensive data checking and verification to identify and resolve the reasons for missing values, inconsistencies, and out-of-range values. Although we anticipate some missing data based on our experience, we will carefully examine whether missingness is completely at random (MCAR), at random (MAR) or informative (MNAR). Models proposed for analysis can handle incomplete data but do require at least that missingness be at random. Modelling will consider using multiple imputation techniques of covariates to reduce potential biases.

Recruitment/Retention

To assess recruitment, we will track the number of eligible patients presenting to the ED during the time of enrolling sessions and the proportion who agree to participate. Basic demographics and presenting complaint will be collected for all eligible patients, allowing us to identify subgroups who are more or less likely to participate. Similarly approaches will be used to assess rates of loss to follow up at all data collection points. We will assess variables across different patient groups (including age, race, sex), and across the study arms as well as overall and by sites.

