3. UCSD

SECTION 1 – Patient Identifiers. Automatically generate sequential numbers when adding a new patient. Verify MRN has not previously been randomized; if MRN has, auto populate exclusion with “yes”.

1. Name: [FREE TEXT]
2. MRN: Numerical character limit of 8
3. Date of ED visit / screening

SECTION 2 – Inclusion / Exclusion Criteria To be completed by research coordinator per EHR / patient report.

Yes	No	
		Inclusion Criteria – ALL must be “Yes”
x		1. ≥ 18 years of age
x		2. Ability to communicate in English
x		3. Level 3, 4, 5 on triage rate scale
x		4. Acute musculoskeletal, back, pelvic, non-cardiac chest, abdominal, and headache pain (≥ 4 on the NRS) due to non-penetrating injury.
		Exclusion Criteria – ALL Must be “No”
x		5. Fever exceeding 100° F
x		6. Presenting with a chief complaint of a psychological / psychiatric concern
x		7. Presenting with chief complaint of Migraine
x		8. Current Pregnancy
x		9. Self-reported or documented opioid medication taken orally within 4 hours
x		10. Presenting with chief complaint of Joint Dislocation
x		11. Presenting with chief complaint of Bone Fracture
x		12. Confirmed or suspected COVID-19

1. Participant’s status based on the screening?
 - a. Eligible
 - b. Non eligible
 - c. Unable to ascertain

SECTION 3 – Provider Verification To be completed by research coordinator

1. Is the Provider Sign Off form completed and signed?

- a. Yes
- b. No **(END PROCESS)**

- c. Did not receive from Provider **(END PROCESS)**
 - i. If yes, what is the patient's status per the ED provider?
 - 1. Eligible
 - 2. Not eligible
 - a. If not eligible, what reason was indicated? **(END PROCESS)** [FREE TEXT]

SECTION 4 – Consent To be completed by research coordinator.

- 1. Did the patient consent to participate?
 - a. Yes
 - i. If yes, which follow up method did they choose?
 - 1. Phone/text: 10 digit verification
 - 2. Email: [FREE TEXT]
 - 3. Both: 10 digit verification and free text (IDEAL)
 - b. No
 - i. Reason for refusal? **(END PROCESS)**
 - 1. Not interested in study
 - 2. Study will take too much time
 - 3. Family present
 - 4. Acupuncture or needle fear
 - 5. OTHER [FREE TEXT]
- 2. Did the patient share their mailing address for remuneration?
 - a. Yes
 - i. If yes, please enter: [FREE TEXT]
 - b. No

BASELINE FORM – CHECK TO BE SURE THAT Consent section is “yes”.

SECTION 1 – Baseline Questions To be asked and entered by research coordinator/assistant, not blinded.

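### The primary recruitment rate is defined differently in 9.5.1 and 9.6, and both read enrolled/eligible as willingness without recording who was approached

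*Combined protocol and SAP*

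**What the plan says.** Section 3 names recruitment and retention as the primary outcomes. Four places define recruitment:

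- Section 9.5 (Feasibility of Recruitment and Retention): "We will assess recruitment rates (# enrolled / # eligible", with no time frame for the denominator.
- Section 9.5.1 (Primary Outcome): "we will track the number of eligible patients presenting to the ED during the time of enrolling sessions and the proportion who agree".
- Section 9.6, Aim 2a: "we will track the number of eligible patients presenting to the ED and the proportion who agree to participate".
- Section 9.6, Table 1: "recruited patients / # eligible".

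Sections 9.5.1 and 9.6 add that demographics and presenting complaint will be collected for every eligible patient, so that groups with higher or lower participation can be identified.

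Under sections 4.3 and 6.2.1, staff approach a patient only after rooming, examination by the ED provider and a signed approval form. In the Appendix B screening form, Section 2 records eligibility, Section 3 records the provider sign-off, and Section 4 asks "Did the patient consent to participate". Section 4 allows Yes, or No followed by a reason for declining. Section 4.3 also promises a log that covers eligible candidates who did not take part.

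**The concern.** There are two linked problems. First, 9.5.1 restricts the denominator to staffed sessions and 9.6 does not, although they describe the same primary outcome in otherwise near-identical terms.

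Second, both sections call the ratio the share who agree. Agreement can be observed only in someone who was asked. An eligible patient who was discharged, moved or passed over before staff arrived adds one to the denominator and nothing to the numerator, exactly as a refusal does.

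The stated purpose of the study is to refine procedures for a larger trial, and low reach and low consent call for different responses. Section 9.5 (Potential Challenges) offers a longer recruitment period or more enrolling hours. Both add chances to approach patients; neither changes what patients are asked to accept. Session times vary across sites, and 9.6 plans to explain site differences in recruitment through qualitative data. A difference in reach could therefore be interpreted as a difference in attitude.

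**Working it through.** **1. The plan's own figures.** Section 2.2 gives 46 consenting of 59 eligible in the pilot RCT: 46/59 = 78.0% (exact 95% CI 65.3 to 87.7), as stated. It gives 248 of 279 approached patients consenting in Observational Study 1: 248/279 = 88.9% (84.6 to 92.3), stated as 89%. Both reproduce.

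**2. The definitions side by side.**

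| Place | Numerator | Denominator | Limited to sessions? |
|---|---|---|---|
| 9.5 | enrolled | eligible | not stated |
| 9.5.1 | agree | eligible, presenting | yes |
| 9.6 Aim 2a | agree | eligible, presenting | no |
| 9.6 Table 1 | recruited | eligible | not stated |

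None uses an approached count. The word recruited also shifts: Table 1 makes it the numerator for recruitment and then the denominator for provider adoption, whereas 9.5 measures adoption against eligible patients. That 9.5 wording implies that eligible is counted before provider approval.

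**3. What the ratio measures.** Let a be the share of eligible patients approached and w the share of approached patients who enroll. An unapproached patient cannot enroll, so enrolled/eligible = a × w. This equals w only when a = 1 and is lower otherwise.

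**4. An illustration from the documents.** Observational Study 1 reports the approach step: "Of 436 patients referred, 279 were approached by the acupuncturist during their ED visit". Then a = 279/436 = 64.0% (59.3 to 68.5), w = 88.9%, and the product is 248/436 = 56.9% (52.1 to 61.6). The denominator alone moves the figure by 88.9 − 56.9 = 32.0 percentage points. The 436 were referred by providers, not screened as eligible, so this shows the mechanism and does not estimate a for this trial.

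**5. A range for this trial.** The documents give no approach share, so a is assumed. Taking w = 0.78 as a stand-in (also an assumption, because section 2.2 does not say whether all 59 eligible pilot patients were approached):

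| a | enrolled/eligible = a × 0.78 |
|---|---|
| 1.0 | 78% |
| 0.9 | 70% |
| 0.8 | 62% |
| 0.64 | 50% |
| 0.5 | 39% |

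Enrolled/approached is 78% in every row. Two sites with equal willingness but a = 0.9 and a = 0.6 would show 0.9 × 0.78 = 70% and 0.6 × 0.78 = 47%.

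**6. Tracing an unapproached patient through the form.** If the sign-off is missing, not returned or negative, Section 3 records that and the process ends, so the patient is identifiable and never reaches the consent item. If the provider clears the patient and staff then miss them, Section 4 has no matching answer. The case could be seen only as a blank section, as free text under a refusal, or in the log.

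**The case against.** The strongest reply is that enrolled/eligible is a legitimate recruitment measure. It gives the yield that a future trial needs for planning, and section 2.2 itself speaks of recruitment and reach together. That stands: the measure misleads only when it is read as willingness, although 9.5.1 and 9.6 invite that reading.

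A reader might infer that the form cannot distinguish unapproached patients from refusals at all. It can for those stopped at sign-off, and the log may hold reasons for others. Provider adoption, as 9.5 defines it, also separates part of the loss. The gap is confined to provider-cleared patients who were then missed, and to the absence of any planned rate that uses this information.

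A reader might also infer that the result could not be compared with the 78% and 50% planning values. Those values use eligible patients as the denominator too, so enrolled/eligible matches them on that point. It is enrolled/approached that has no pilot counterpart.

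Finally, one could read 9.6 as counting patients at all hours, although each site is "staffing an average 2.5, 4-6 hour recruitment/intervention sessions per week". The primary-outcome section expressly says "the number of eligible patients presenting to the ED during the time of enrolling sessions", and eligibility depends on screening by on-site staff. Patients outside sessions could enter only through the administrative data that 9.6 mentions without specifying. This is best treated as a wording conflict, not as evidence of a severe bias.

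**Conclusion.** The point holds in a limited form. The primary recruitment measure has inconsistent definitions, and its description as agreement mixes reach with willingness. The direction is certain: every eligible patient left unapproached lowers the apparent share who agree. The size is unknown, because no document gives an approach share or a missed-approach rate for this trial; if everyone eligible is approached, the understatement is zero. The 32-point gap in Observational Study 1 is illustrative only, and the 39% to 78% range rests on assumed approach shares and an assumed 78% consent rate. The documents do not support calling the planned rate invalid. They support completing it, and doing so is worthwhile because recruitment is what this feasibility trial sets out to measure.

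**What to change.** 1. Add the enrolling-session limit to 9.6 Aim 2a, and use one definition in 9.5, 9.5.1, 9.6 and Table 1: enrolled (consented and randomized, as in 6.2.2) divided by eligible patients presenting during staffed sessions. State whether eligible means the Section 2 screening result or the status after provider sign-off.
2. Add one REDCap item before the consent question: *Approached for consent? Yes / No, with reason* (for example, left before approach, staff with another participant, session ended).
3. Report approached/eligible and enrolled/approached beside enrolled/eligible, overall and by site, with the exact 95% confidence intervals already planned in 9.5. Describe enrolled/eligible as reach, and base statements about willingness on enrolled/approached.

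The cost is one phrase, one form item, two extra rows in the recruitment table and one more entry per eligible patient. For anyone screened before the item exists, the section 4.3 log can be used as far as its recorded reasons allow.
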